8.0 Efficacy Analyses

Rome III criteria will be assessed by the investigator at the Screening Visit (Visit 1), and at the end of the study intervention period at the EOT Visit (Visit 7 for FC participants and Visit 10 for IBS-C participants) as an additional efficacy assessment. The counts and percentages will be provided for participants who no longer fulfill Rome III criteria at the screening visit and the end of study intervention period in this study. No missing data will be imputed, and data as observed will be summarized. Fulfillment of Rome III criteria data will be presented in the listing.

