8.1. Efficacy Assessments

Rome III criteria will be assessed by the investigator at the Screening Visit (Visit 1) and at the end of the study intervention period at the EOT Visit (Visit 7 for FC participants and Visit 10 for IBS-C participants) as an additional efficacy assessment.

- For participants who enroll in LIN-MD-66 within \leq 28 days since last study intervention in lead-in study LIN-MD-64, the Week 12 Visit/EOT Rome III assessment will be used as the Screening Visit assessment in LIN-MD-66.
- For participants who enroll in LIN-MD-66 after $>$ 28 days from last study intervention in their lead-in study, Rome III assessment at Screening will be assessed over the 2 month period immediately prior to the LIN-MD-66 Screening Visit (Visit 1), or over the 1 month period immediately prior to the LIN-MD-66 Screening Visit if 2 months have not elapsed.

A participant will be considered as fulfilling Rome III criteria if a “yes” response is recorded to the overall question of whether the participant meets Rome III criteria for FC or IBS-C. For the EOT assessment, the criteria will be assessed over the last 4 weeks of the study intervention period. In the event a participant discontinues the study prematurely, these criteria will be assessed over the last 4 weeks of study intervention, or over the duration of study intervention if less than 4 weeks.

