3.0 Endpoints

3.1 Efficacy Endpoint

There is one other efficacy endpoint in this study:

- The achievement of no longer fulfilling Rome III criteria at the end of study intervention period

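### SAP 8.0 reports Rome III status at Screening and EOT as two separate percentages with no stated reference point or denominator, so conversion during LIN-MD-66 cannot be read from them

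*SAP*

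**What the plan says.** SAP 3.1 says "There is one other efficacy endpoint in this study" and defines it as "The achievement of no longer fulfilling Rome III criteria at the end of study intervention period". This describes a change of status, but SAP 3.1 does not say from when.

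SAP 8.0 states: "The counts and percentages will be provided for participants who no longer fulfill Rome III criteria at the screening visit", and the same sentence adds the end of the intervention period as a second timepoint. It goes on: "No missing data will be imputed, and data as observed will be summarized". No cross-tabulation of the two visits is described, and no denominator is stated beyond the reference to observed data. Individual Rome III status goes into a listing. Protocol 9.4 leaves the summary of this endpoint to the SAP.

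The source of the Screening value depends on how the child enters (Protocol 8.1 and Tables 1-1 to 1-4):

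- LIN-MD-64 completers enrolling within 28 days: "the Week 12 Visit/EOT Rome III assessment will be used as the Screening Visit assessment in LIN-MD-66".
- All completers enrolling after 28 days: a new assessment at Screening, looking back 2 months, or 1 month if 2 have not passed.
- LIN-MD-63 completers enrolling within 28 days: no stated source. Table 1-3 has no Rome III entry at Screening, and the carry-forward rule in Protocol 8.1 names LIN-MD-64 only.

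At EOT, "the criteria will be assessed over the last 4 weeks of the study intervention period". Early leavers are scored over their last 4 weeks on study drug, or over their whole exposure if it was shorter.

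No current inclusion criterion in Protocol 5.1 requires that Rome III is met on entry to LIN-MD-66.

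**The concern.** A child can enter LIN-MD-66 already not meeting Rome III. For a LIN-MD-64 completer enrolling within 28 days, the Screening status was recorded after 12 weeks of double-blind lead-in intervention (Protocol 4.1). Some FC children received placebo in that period, as the LIN-MD-64 title in Protocol 2 and the disposition table in SAP 5.0 show. If such a child still does not meet the criteria at EOT, the child counts in the EOT percentage, although nothing changed during this study.

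The EOT figure therefore mixes two groups: children who converted during the 24 or 52 weeks, and children who arrived without the criteria and stayed so. The Screening percentage printed beside it gives the net movement but not the flows. In a long-term extension, the informative quantities are how many children newly stop meeting the criteria and how many relapse. The plan describes neither, and this is the study's only efficacy endpoint.

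**Working it through.** The plan has no figure to reproduce: no response rate, effect size, dropout rate or power is given, and Protocol 9.2 says that the planned enrolment of at least 120 has no statistical basis. The check therefore uses identities with assumed inputs.

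**1. EOT percentage against conversion.** Let

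- s = share not meeting Rome III at Screening,
- k = share of those who still do not meet it at EOT (persistence),
- r = share of those meeting it at Screening who do not at EOT (conversion).

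With no missing data, the reported EOT share is p = s·k + (1 − s)·r, so p − r = s(k − r).

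| s | k | r | p = s·k + (1 − s)·r | p − r |
|---|---|---|---|---|
| 0.1 | 0.9 | 0.4 | 0.09 + 0.36 = 0.45 | +5 points |
| 0.3 | 0.9 | 0.4 | 0.27 + 0.28 = 0.55 | +15 points |
| 0.5 | 0.9 | 0.4 | 0.45 + 0.20 = 0.65 | +25 points |
| 0.3 | 0.5 | 0.6 | 0.15 + 0.42 = 0.57 | −3 points |

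At s = 0 the difference is zero. Over s from 0 to 0.7, k from 0.7 to 1.0 and r from 0.2 to 0.6, it runs from 0 to 0.7 × (1.0 − 0.2) = 0.56, or +56 points. That range is never negative only because k was taken above r throughout. The fourth row shows the sign reversing when conversion exceeds persistence.

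**2. What two marginal percentages can show.** Suppose the table prints 50% at Screening and 65% at EOT. Then 0.5k + 0.5r = 0.65, so k + r = 1.3. This fits equally well with:

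- r = 30% and k = 100%: modest conversion, no relapse;
- r = 40% and k = 90%: 10% relapse;
- r = 100% and k = 30%: complete conversion, 70% relapse.

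The printed figures do not distinguish these cases. With s = 0.7, k = 0.9 and r = 0.2, the table would show 70% and then 0.63 + 0.06 = 69%, almost no change, although 20% of those who could convert did so and 10% of the others relapsed. On observed data the two percentages may also rest on different children, so even the net difference need not be within-child.

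**3. Missing EOT assessments.** If a fraction m has no EOT assessment and the observed share is p_obs, counting the missing as still meeting the criteria gives p_obs(1 − m), a drop of p_obs·m. Counting them all as not meeting the criteria gives p_obs(1 − m) + m.

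| p_obs | m | Missing as still meeting | Missing as not meeting |
|---|---|---|---|
| 60% | 5% | 57% | 62% |
| 60% | 10% | 54% | 64% |
| 60% | 20% | 48% | 68% |
| 40% | 5% | 38% | 43% |
| 40% | 20% | 32% | 52% |

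The drop is 2 to 12 points for m = 5% to 20% and p_obs = 40% to 60%.

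**The case against.** A reader might infer that the EOT percentage overstates the benefit of long-term treatment. The documents do not support that reading. They give none of s, k, r or m, and the sign of s(k − r) depends on values nobody has yet. The entry level is also disclosed: SAP 8.0 reports Screening beside EOT and lists individual status. And there is no control arm, hypothesis or test (Protocol 9.1, Appendix 6; SAP 11.0), so no treatment effect is formally estimated. This objection stands.

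The reference point may also be intended as lead-in entry. SAP 8.0 counts children who have stopped meeting the criteria at Screening itself, which makes sense only against something earlier. The LIN-MD-62 and LIN-MD-63 titles require Rome III or modified Rome III, and the rationale closing Protocol 5.2 describes the population in those terms. On that reading, counting a child who stopped meeting the criteria during the lead-in is correct. This is the likelier reading, but the SAP does not state it. SAP 9.1 sets a baseline for laboratory values, vital signs, weight, height and ECG, and none for Rome III. The EOT figure is then status since lead-in entry and needs that label.

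A reader might also infer that children leaving for lack of efficacy inflate the figure. Protocol 7.1.1 requires early leavers to attend EOT and has non-attenders asked in writing, the EOT visit includes Rome III, and Protocol 8.1 scores them over their last weeks on drug. Only children with no EOT assessment at all are lost, so this is the smaller concern, though Protocol 7.3 foresees some loss to follow-up.

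Finally, SAP 1.0 places table specifications in a separate document, which may contain a shift table. The reference point and denominator still belong in the SAP.

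**Conclusion.** The point holds as one of definition and presentation. SAP 8.0 summarises a change of status as two separate observed-data percentages, with no stated reference point or denominator. Because entry does not require that Rome III is met, and many Screening values may be lead-in EOT results, the EOT percentage is a cumulative status that can include lead-in response. It can differ from conversion in LIN-MD-66 in either direction, by s(k − r): upward if persistence exceeds conversion, downward otherwise. In the worked cases the difference was −3 to +25 points, and up to +56 at the edge of the assumed range. These sizes are illustrations, not estimates. New conversion and relapse cannot be separated from the planned percentages whatever the values turn out to be.

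The endpoint is descriptive, labelled as other, and secondary to a safety objective. This is a cheap and worthwhile improvement, not a threat to the study's main conclusions.

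**What to change.** In SAP 8.0:

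1. State the reference point, and label the all-participant EOT percentage as status relative to lead-in entry.
2. Add a Screening-by-EOT shift table with a missing category at each visit, separately for FC and IBS-C.
3. Beside the all-participant figure, report the EOT percentage among participants meeting Rome III at Screening, with its denominator.
4. Add one sensitivity row that counts a missing EOT assessment as still meeting the criteria.
5. Show LIN-MD-63 completers enrolling within 28 days as missing at Screening, because Table 1-3 and Protocol 8.1 give no source for their value.

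The cost is SAP wording and one extra table. No new data and no protocol change are needed. The restricted percentage will have a smaller denominator and may be less favourable than the all-participant figure.

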9.0 Safety Analyses

9.1 General Considerations

All safety analyses or summaries will be performed by study intervention group using the safety population, for overall and for each age group (6 to 11 years and 12 to 18 years in FC; 7 to 11 years and 12 to 18 years in IBS-C) separately for FC and IBS-C participants.

For each safety parameter (laboratory, vital signs, body weight, height, and ECG), the baseline will be defined as below:

- If participants enroll into LIN-MD-66 within 28 days of last dose date of the lead-in study, baseline of the lead-in study will be used as the baseline value in LIN-MD-66.
- If participants enroll into LIN-MD-66 after 28 days of last dose date of the lead-in study, the last non-missing assessment made before the first dose of the study intervention in this study will be used as the baseline value in LIN-MD-66.

Safety data analyses will be provided descriptively based on the observed safety data, without data imputation for missing safety parameters.

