4.3. Justification for Doses

The linaclotide dosages chosen for FC participants in this long-term safety study (72 and 145 µg) were well tolerated among participants 6 to 17 years of age with FC in LIN-MD-62. The safety profile was consistent with prior adult linaclotide studies for CIC. FC participants 6 to 17 years of

age who complete either LIN-MD-62 or LIN-MD-64, will have the option to enroll into this study. FC participants, 6 to 11 years of age, will receive open-label 72 µg linaclotide. FC participants, 12 to 17 years of age, will be randomly assigned open-label linaclotide at a 1:1 ratio to 72 µg linaclotide or 145 µg linaclotide.

The linaclotide doses of 290 µg or 145 µg once daily chosen for IBS-C participants in this long-term safety study were well tolerated among participants 12 to 17 years of age (290 µg dose) and 6 to 17 years of age (145 µg dose) with IBS-C in LIN-MD-63. The safety profile was consistent with prior adult linaclotide studies for IBS-C. While the 290 µg linaclotide dose is the highest dose being evaluated in IBS-C participants 6 to 17 years of age in the lead-in Phase 3 study LIN-MD-64, LIN-MD-63 completers who received ≤ 145 µg linaclotide or placebo in LIN-MD-63 will have the option to receive open-label linaclotide 145 µg once daily for 52 weeks. LIN-MD-64 completers with IBS-C will have the option to either remain on the same blinded linaclotide dose they were receiving in lead-in study LIN-MD-64 (blinded linaclotide 290 µg or 145 µg once daily) or to receive open-label linaclotide 290 µg once daily.

Dose modifications permitted for FC and IBS-C participants are described in Section [6.6](#).

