6.3. Measures to Minimize Bias: Randomization and Blinding

Participants with FC, 12 to 17 years of age, will be randomly assigned at a 1:1 ratio to 72 µg linaclotide or 145 µg linaclotide.

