9.4. Statistical Analyses

The Statistical Analysis Plan (SAP) will be developed and finalized before database lock.

The summary of the other efficacy endpoint of proportion of participants who no longer fulfill Rome III criteria at the end of the study intervention period will be discussed in the SAP.

This section is a summary of the planned statistical analyses for safety. Further details will be included in the SAP. All safety analyses or summaries will be performed using the Safety Population, for overall and for each age group (unless mentioned otherwise) by study intervention group separately for the FC and IBS-C pediatric populations.

The safety parameters will include AEs, clinical laboratory parameters, vital sign measurements, weight, height, and ECG parameters. For each safety parameter, the baseline value for all analyses of the corresponding safety parameter (laboratory, vital signs, body weight, height, and ECG) will be defined as below:

- 1) If participants enroll into LIN-MD-66 within 28 days of last dose date of the lead-in study, baseline of the lead-in study will be used as the baseline value in LIN-MD-66.
- 2) If participants enroll into LIN-MD-66 after 28 days of last dose date of the lead-in study, the last non-missing assessment made before the first dose of study intervention in this study will be used as the baseline value in LIN-MD-66.

Safety data analyses will be provided descriptively based on the observed safety data, without data imputation for missing safety parameter assessment(s).

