10.6. Appendix 6: Study Tabular Summary

Parameter Group	Parameter	Value
Trial information	Trial Title	A Long-term Safety Study of Oral Linaclootide Administered to Pediatric Participants with Functional Constipation (FC) or Irritable Bowel Syndrome with Constipation (IBS-C)
	Clinical Study Sponsor	Allergan Sales LLC
	Trial Phase Classification	Extension Study
	Trial Indication	FC and IBS-C
	Trial Indication Type	Study intervention
	Trial Type	Safety
	Trial Length	24 weeks (FC participants) 52 weeks (IBS-C participants)
	Planned Country of Investigational Sites	United States of America (USA), Canada, Europe, and the Middle East
	Planned Number of Participants	At least 120
	FDA-Regulated Device Study	No
Participant information	FDA-Regulated Drug Study	Yes
	Pediatric Study	Yes
	Diagnosis Group	Pediatric participants with FC or IBS-C; specifically, participants who have completed study intervention in Phase 2 Studies LIN-MD-62, LIN-MD-63 or Phase 3 Study LIN-MD-64
	Healthy Participant Indicator	No
	Planned Minimum Age of Participants	6 years
	Planned Maximum Age of Participants	18 years
	Sex of Participants	Both
	Stable Disease Minimum Duration	Not applicable

Parameter Group	Parameter	Value
Treatments	Investigational Therapy or Treatment	Linaclootide
	Intervention Type	Drug
	Pharmacological Class of Invest. Therapy	Agonist of guanylate cyclase C
	Dose per Administration	Single
	Dose Units	72 µg, 145 µg, or 290 µg
	Dosing Frequency	Once daily
	Route of Administration	Oral
	Current Therapy or Treatment	None
	Added on to Existing Treatments	No
	Control Type	None
Trial design	Comparative Treatment Name	Not applicable
	Study Type	Interventional
	Intervention Model	Open-label and blinded
	Planned Number of Arms	2 arms for FC participants: open-label 72 and 145 µg 4 arms for IBS-C participants: 2 arms for open-label (145 and 290 µg) and 2 arms for blinded (145 and 290 µg)
	Trial is Randomized	Applicable to FC participants 12 to 17 years of age only: will be randomly assigned at 1:1 ratio to 72 µg linaclootide or 145 µg linaclootide
	Randomization Quotient	Not applicable
	Trial Blinding Schema	Open-label and blinded
	Stratification Factor	None
	Adaptive Design	No

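### FC overall safety tables confound dose with age, and the planned adolescent tables that set 72 beside 145 µg are grouped by majority dose received, not by randomised dose

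*SAP*

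**What the plan says.** Allocation in FC depends on age. Protocol 4.3: "FC participants, 6 to 11 years of age, will receive open-label 72 µg linaclotide". Protocol 6.3: "Participants with FC, 12 to 17 years of age, will be randomly assigned at a 1:1 ratio to" 72 µg or 145 µg. Protocol Appendix 6 confirms that this is the only randomisation in the study: "Applicable to FC participants 12 to 17 years of age only: will be randomly assigned at 1:1 ratio to" the two doses.

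On display, SAP 9.1 says "All safety analyses or summaries will be performed by study intervention group using the safety population, for overall and for each age group", and the sentence goes on to define the age groups: "6 to 11 years and 12 to 18 years in FC; 7 to 11 years and 12 to 18 years in IBS-C) separately for FC"; IBS-C is likewise tabulated apart. Protocol 9.4 gives the same rule: "for overall and for each age group (unless mentioned otherwise) by study intervention group separately for the FC and IBS-C pediatric populations". So each FC safety summary appears by dose three times: overall, at ages 6-11 and at ages 12-18.

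On grouping, SAP 4.0 places each participant under the dose actually received. Where that differs from the assigned dose, the dose taken for the majority of the intervention period counts, with ties going to the higher dose. It states that this also covers participants whose dose is reduced or raised during the study. Protocol 6.6 and SAP 2.3 allow an FC participant on 145 µg to be reduced to 72 µg after an intolerable adverse event (AE). SAP 11.0 rules out inferential testing.

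**The concern.** Two separate distortions affect how a reader will see dose in FC.

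The first is age. The overall 145 µg column contains adolescents only. The overall 72 µg column contains the other randomised adolescents plus every younger child. Any outcome that varies with age will differ between these columns without a dose effect. The SAP itself treats age as relevant: Appendix B sets age-specific limits for alkaline phosphatase, supine blood pressure and pulse, QRS and PR. Nothing in the SAP text warns against comparing the overall columns.

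The second is the majority-dose rule. The FC 12-18 tables are free of the age problem, but a participant can be reclassified because of an AE. An adolescent randomised to 145 µg who is reduced early is counted under 72 µg, together with the event that led to the reduction. This bears on tolerability outcomes such as diarrhea, which Protocol 8.3 singles out for particular attention.

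At stake is whether the study report gives a sound description of how safety differs between the two FC doses.

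**Working it through.** The documents give no figure to reproduce: the sample size has no statistical basis (SAP 2.4), and neither the FC age split nor event rates by age are stated. Inputs from the documents are the allocation rule, the display rule and the majority-dose rule. Everything else below is assumed.

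**Age mix of the overall columns.** Let f be the share of FC participants aged 6-11. With exact 1:1 allocation and no dose changes:
- 72 µg column, as a share of FC: f + (1 − f)/2 = (1 + f)/2
- share of that column aged 6-11: w = f ÷ [(1 + f)/2] = 2f/(1 + f)
- share of the 145 µg column aged 6-11: 0

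Results: f = 20%, w = 0.4/1.2 = 33%; f = 50%, w = 1.0/1.5 = 67%; f = 70%, w = 1.4/1.7 = 82%.

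**Difference due to age alone.** With no dose effect, 72 µg minus 145 µg in the overall table = w × (risk at 6-11 − risk at 12-18). For assumed risks 5 points apart:
- f = 20%: 0.333 × 5 = 1.7 points
- f = 50%: 0.667 × 5 = 3.3 points
- f = 70%: 0.824 × 5 = 4.1 points

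The sign follows whichever age group has the higher risk. Take 30 children and 30 adolescents:
- Risks 10% (6-11) and 5% (12-18), no dose effect: 72 µg = (30 × 0.10 + 15 × 0.05)/45 = 8.3%, against 5.0% for 145 µg.
- Same risks, but 145 µg doubles the adolescent risk to 10%: 8.3% against 10.0%, a ratio of 1.2 where the true ratio is 2.0.
- Risks swapped to 5% and 10%, no dose effect: (30 × 0.05 + 15 × 0.10)/45 = 6.7%, against 10.0%.

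In the FC 12-18 table w = 0 in both columns, so this difference is 0 at every f.

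**Majority-dose rule in the FC 12-18 table.** For a participant who completes 24 weeks (168 days), fewer than 84 days on 145 µg places them under 72 µg. Assume 50 adolescents randomised per arm, with only participants who have the event reclassified.

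| True risk, 72 / 145 µg | Share of 145 µg events moved | Table shows 72 µg | Table shows 145 µg |
|---|---|---|---|
| 8% / 8% | one quarter (1 of 4) | 5/51 = 9.8% | 3/49 = 6.1% |
| 8% / 8% | one half (2 of 4) | 6/52 = 11.5% | 2/48 = 4.2% |
| 8% / 16% | one quarter (2 of 8) | 6/52 = 11.5% | 6/48 = 12.5% |
| 8% / 16% | one half (4 of 8) | 8/54 = 14.8% | 4/46 = 8.7% |

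This movement is one-way in FC, because 72 µg has no lower dose level. A true 8-point excess on 145 µg shrinks to 1 point when a quarter of the events move, and reverses when half do.

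**The case against.** A reader might infer that the randomised comparison is not used at all. The documents do not support that. SAP 9.1 and Protocol 9.4 both require every safety summary by dose within FC 12-18, so the two adolescent groups do appear side by side. The same age split applies to disposition, exposure, compliance, demographics, medical history, medications and protocol deviations.

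A reader might also infer a known direction, such as an inverse dose response for diarrhea. That is not supported either. Protocol 2.2.2 reports diarrhea in 7.6% of linaclotide-treated participants in LIN-MD-62 but gives no incidence by age, and swapping the assumed risks swaps the sign.

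The strongest counter-argument is that dose comparison is not an objective. There are no hypotheses, no testing and no statistical sample size, so descriptive columns without differences or intervals fit the study. Table specifications also sit in a separate document (SAP 1.0), which may carry footnotes. Age-specific limits already deal with part of the age effect on laboratory, vital-sign and ECG flags. Replacing the overall dose columns with one pooled column would depart from Protocol 9.4 and lose the pooled 72 µg exposure base, which is useful for rare events.

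Much of this stands. It argues for keeping the overall columns and against any claim of a missing inferential analysis. It does not answer the two points that remain: tables by dose invite a dose reading whether or not a test is planned, and the majority-dose rule is written into the SAP itself, where no table footnote would undo the reclassification.

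**Conclusion.** The concern holds in two parts. First, the FC overall tables confound dose with age by design, and the SAP text carries no caution. Second, the FC 12-18 tables remove that confounding but are grouped by majority dose received, so they are not strictly as randomised, and no difference or interval accompanies them.

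That the overall columns differ in age mix follows from the allocation rule alone; how far depends on the unknown split. The illustrated distortions (1.7 to 4.1 points from age; 9.8% against 6.1% from reclassifying one event in four) rest on assumed age splits, event rates, arm sizes and reduction patterns. Their real size is unknown, as is the direction of the age effect. The problem is one of presentation and grouping, and it does not undermine the study's stated objective.

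**What to change.** 1. Keep the FC overall dose columns. Add a footnote that they differ in age mix because all participants aged 6-11 are assigned 72 µg, and that they are not a dose comparison.
2. In SAP 9.1, name the FC 12-18 table by randomised (initially assigned) dose as the dose comparison, shown alongside the planned table by dose received.
3. For that table, add the risk difference (145 minus 72 µg) with a 95% confidence interval for any treatment-emergent AE, diarrhea, and AEs leading to discontinuation. Label these descriptive. SAP 11.0 bars testing, not intervals.

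The cost is one additional adolescent display and three intervals, with no new data. The intervals will be wide if the arms are small. With 15 per arm and risks of 5% and 10%, the half-width is 1.96 × √(0.05 × 0.95/15 + 0.10 × 0.90/15) = 1.96 × 0.096, about 19 points. That width would itself tell readers how little the adolescent comparison can establish.
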